### **2.1.1.3 Lesions that split or coalesce on treatment**

When non-nodal lesions ‘fragment’, the longest diameters of the fragmented portions should be added together to calculate the target lesion sum. Similarly, as lesions coalesce, a plane between them may be maintained that would aid in obtaining maximal diameter measurements of each individual lesion. If the lesions have truly coalesced such that they are no longer separable, the

vector of the longest diameter in this instance should be the maximal longest diameter for the ‘coalesced lesion’.

## 2.2 Evaluation of Non-Target Lesions

This section provides the definitions of the criteria used to determine the tumor response for the group of non-target lesions. While some non-target lesions may actually be measurable, they need not be measured and instead should be assessed only qualitatively at the time points specified in the protocol.

- **Complete Response (CR):** Disappearance of all non-target lesions. All lymph nodes must be non-pathological in size (< 10mm short axis).
- **Non-CR/Non-PD:** Persistence of one or more non-target lesion(s)
- **Progressive Disease (PD):** Unequivocal progression (see below) of existing non-target lesions.

### 2.2.1 *Special Notes on Assessment of Progression of Non-Target Disease*

The concept of progression of non-target disease requires additional explanation as follows:

#### 2.2.1.1 *When the patient also has measurable disease*

In this setting, to achieve ‘unequivocal progression’ on the basis of the non-target disease, there must be an overall level of substantial worsening in non-target disease such that, even in presence of SD or PR in target disease, the overall tumor burden has increased sufficiently to merit discontinuation of therapy (see examples in [Appendix 2](#) and further details below). A modest ‘increase’ in the size of one or more non-target lesions is usually not sufficient to qualify for unequivocal progression status. Pleural effusions, pericardial effusions and ascites will not be followed as target or non-target lesions and will not contribute to response or progression. The designation of overall progression solely on the basis of change in non-target disease in the face of SD or PR of target disease will therefore be extremely rare.

#### 2.2.1.2 *When the patient has only non-measurable disease*

This circumstance arises in some trials when it is not a criterion of study entry to have measurable disease. The same general concepts apply here as noted above, however, in this instance there is no measurable disease assessment to factor into the interpretation of an increase in non-measurable disease burden. Because worsening in non-target disease cannot be easily quantified (by definition: if all lesions are truly non-measurable) a useful test that can be applied when assessing patients for unequivocal progression is to consider if the increase in overall disease burden based on the change in non-measurable disease is comparable in magnitude to the increase that would be required to declare PD for measurable disease: i.e., an increase in tumor burden representing an additional 73% increase in ‘volume’ (which is equivalent to a 20% increase diameter in a measurable lesion). Examples include, an increase in lymphangitic disease from localized to widespread, or may be described as ‘sufficient to require a change in therapy’. If ‘unequivocal progression’ is seen, the patient should be considered to have had overall PD at that point. While it would be ideal to have

objective criteria to apply to non-measurable disease, the very nature of that disease makes it impossible to do so; therefore the increase must be substantial.

### **2.2.2 New Lesions**

#### New bone lesions

New bone lesions should be evaluated as per PCWG3 criteria. Bone lesions will be assessed by radionuclide bone scan only. Radiographic progression on bone scan is defined by the following criteria:

- At least 2 new lesions on the first posttreatment bone scan, confirmed on the next scan (performed at least 6 weeks later) **AND** with at least two additional lesions as compared to the first post-treatment bone scan. Date of progression is then the date of first post-treatment scan,
- For scans after the first post-treatment scan, at least 2 new lesions relative to the first post-treatment scan **AND** confirmed on a subsequent scan (performed at least 6 weeks later). Date of progression is the date of the scan that first documents at least 2 new lesions relative to the first post-treatment scan.

#### New soft tissue lesions

The appearance of new malignant soft tissue lesions denotes disease progression; therefore, some comments on detection of new lesions are important. There are no specific criteria for the identification of new radiographic lesions; however, the finding of a new lesion should be unequivocal: ie, not attributable to differences in scanning technique, change in imaging modality or findings thought to represent something other than tumor. This is particularly important when the patient's baseline lesions show partial or complete response. For example, necrosis of a liver lesion may be reported on a CT scan report as a 'new' cystic lesion, which it is not.

NOTE: Fluid collections (pleural effusions, pericardial effusions, and ascites) will not be considered new lesions and will not contribute to response or progression. In the event a new fluid collection is seen on a post-baseline imaging exam, a comment may be made, but the appearance of a new fluid collection alone should not result in an assessment of Progressive Disease (PD). A lesion identified on a follow-up study in an anatomical location that was not scanned at baseline is considered a new lesion and will indicate disease progression. An example of this is the patient who has visceral disease at baseline and while on study has a CT or MRI brain ordered which reveals metastases. The patient's brain metastases are considered to be evidence of PD even if he/she did not have brain imaging at baseline. A lesion identified on Chest X-Ray that was not present in prior CT can be considered a new lesion and will result in Progressive Disease (PD).

If a new lesion is equivocal, for example because of its small size, continued follow-up evaluation will clarify if it represents truly new disease. If repeat scans confirm there is definitely a new lesion, then progression should be declared using the date of the initial scan.

## 2.3 Response Assessment

### 2.3.1 Evaluation of Best Overall Response

The best overall response is the best response recorded from the start of the study treatment until disease progression per PCWG3 criteria, or the last response recorded, taking into account any requirement for confirmation and censoring rules regarding subsequent therapy. The patient’s best overall response assignment will depend on the findings of both target and non-target disease and will also take into consideration the appearance of new lesions. Furthermore, depending on the nature of the study and the protocol requirements, it may also require confirmatory measurement.

### 2.3.2 Time Point Response

At each protocol specified time point, a response assessment occurs. Table 2.3.2-1 provides a summary of the overall response status calculation at each time point for patients who have measurable disease at baseline. When patients have non-measurable (therefore non-target) disease only, Table 2.3.2-2 is to be used.

Table 2.3.2-1: Time Point Response: Patients With Target (± Non-Target) Disease			
Target Lesions	Non-Target Lesions	New Lesions	Overall Response
CR	CR	No	CR
CR	Non-CR/non-PD	No	PR
CR	Not evaluated	No	PR
PR	Non-PD or not all evaluated	No	PR
SD	Non-PD or not all evaluated	No	SD
Not all evaluated	Non-PD	No	NE
PD	Any	Yes or No	PD
Any	PD	Yes or No	PD
Any	Any	Yes	PD

CR = complete response, PR = partial response, SD = stable disease, PD = progressive disease and NE = inevaluable

Table 2.3.2-2: Time Point Response: Patients with Non-target Disease Only		
Non-Target Lesions	New Lesions	Overall Response
CR	No	CR
Non-CR/non-PD	No	Non-CR/non-PD a
Not all evaluated	No	NE
Unequivocal PD	Yes or No	PD
Any	Yes	PD
CR = complete response, PD = progressive disease and NE = inevaluable		

a Non-CR/non-PD is preferred over SD for non-target disease since SD is increasingly used as endpoint for assessment of efficacy in some trials so to assign this category when no lesions can be measured is not advised.

### 2.3.3 Best Overall Response

Best response determination of complete or partial response requires confirmation: Complete or partial responses may be claimed only if the criteria for each are met at a subsequent time point of  $\geq 4$  weeks (28 days) later. In this circumstance, the best overall response can be interpreted as in Table 2.3.3-1. When SD is believed to be best response, it must meet the protocol specified minimum time from the date of first treatment or randomization date.

For example, if the first scheduled follow-up imaging visit is Week 6 ( $\pm 7$  days) for a particular protocol, a Best Response of SD can only be made after the subject is on-study for a minimum of 6 weeks (42 days) minus 7 days, for an absolute minimum time on-study of 35 days from the reference start date (reference date is considered Day 1 on study). If the subject is not on-study for at least this amount of time, any tumor assessment indicating stable disease before this time period will have a Best Response of NE unless PD is identified.

**Special note on response assessment:** When nodal disease is included in the sum of target lesions and the nodes decrease to ‘normal’ size ( $< 10$  mm), they may still have a measurement reported on scans. This measurement should be recorded even though the nodes are normal in order not to overstate progression should it be based on increase in size of the nodes. As noted earlier, this means that patients with CR may not have a total sum of ‘zero’ on the case report form (CRF).

Table 2.3.3-1: Best Overall Response (Confirmation of CR&PR Required)		
Overall Response First Time Point	Overall Response Subsequent Time Point	BEST Overall Response
CR	CR	CR
CR	PR	SD, PD OR PR a
CR	SD	SD provided minimum criteria for SD duration met, otherwise, PD
CR	PD	SD provided minimum criteria for SD duration met, otherwise, PD

Table 2.3.3-1: Best Overall Response (Confirmation of CR&PR Required)		
Overall Response First Time Point	Overall Response Subsequent Time Point	BEST Overall Response
CR	NE	SD provided minimum criteria for SD duration met, otherwise, NE
PR	CR	PR
PR	PR	PR
PR	SD	SD
PR	PD	SD provided minimum criteria for SD duration met, otherwise, PD
PR	NE	SD provided minimum criteria for SD duration met, otherwise, NE
NE	NE	NE

CR = complete response, PR = partial response, SD = stable disease, PD = progressive disease, and NE = inevaluable

a If a CR is truly met at first time point, then any disease seen at a subsequent time point, even disease meeting PR criteria relative to baseline, makes the disease PD at that point (since disease must have reappeared after CR). Best response would depend on whether minimum duration for SD was met. However, sometimes ‘CR’ may be claimed when subsequent scans suggest small lesions were likely still present and in fact the patient had PR, not CR at the first time point. Under these circumstances, the original CR should be changed to PR and the best response is PR.

### 2.3.4 Confirmation Scans

**Verification of Response:** To be assigned a status of CR or PR, changes in tumor measurements must be confirmed by consecutive or subsequent repeat assessments that should be performed no less than 28 days after the criteria for response are first met. Subsequent documentation of a CR may provide confirmation of a previously identified CR even with an intervening NE or PR (e.g., CR NE CR or CR PR CR). Subsequent documentation of a PR may provide confirmation of a previously identified PR even with an intervening NE or SD (e.g., PR NE PR or PR SD PR). However, only one (1) intervening time point will be allowed between PR/CRs for confirmation.

**Verification of Progression:** Progression of disease should be verified in cases where progression is equivocal. If repeat scans confirm PD, then progression should be declared using the date of the initial scan. If repeat scans do not confirm PD, then the subject is considered to not have progressive disease.

## APPENDIX 9 STATISTICAL METHODOLOGY

### STATISTICAL DETAILS FOR BAYESIAN LOGISTIC REGRESSION MODEL (BLRM AND BLRM-COPULA) TO GUIDE DOSE ESCALATION AND BASKET DESIGNS TO ASSESS HOMOGENEITY AND FUTILITY IN COHORT EXPANSION

#### 1 MODEL SETUP FOR BMS-986277 MONOTHERAPY

##### 1.1 Methodology Description for Monotherapy

An adaptive 2-parameter Bayesian Logistic Regression Model (BLRM) guided by the escalation with overdose control (EWOC) principle will be used to guide the dose escalation of BMS-986277 monotherapy in the monotherapy phase, providing dose recommendations during dose escalation.

The BLRM will be fitted on the dose-limiting toxicity (DLT) data during the first 6 weeks of treatment accumulated throughout the dose escalation to model the dose-toxicity relationship of BMS-986277 in the monotherapy dose escalation phase.

##### 1.2 Prior Specification for BMS-986277 Monotherapy

The Bayesian approach requires the specification of prior distributions for model parameters, which include parameters  $(\alpha_1, \beta_1)$  for BMS-986277. A mixture prior will be used for parameters  $(\alpha_1, \beta_1)$  for BMS-986277. There are two bivariate normal components in generating this mixture prior:

- Meta-analytic predictive (MAP) component: Obtained based on the clinical safety and exposure profiles of enadenotucirev using the MAP approach, because BMS-986277 is the genetically modified form of enadenotucirev.
- Weakly informative prior for BMS-986277 component: Reflecting the potential higher toxicity of BMS-986277 than enadenotucirev from activating T-cells and allowing for considerable prior uncertainty.

Derivation of prior distribution of these parameters is provided in the following subsections.

##### 1.2.1 *Meta-analytic Predictive Component*

The MAP component provides a prediction of the dose-toxicity curve for BMS-986277 based on prior data from enadenotucirev. This dose-toxicity curve combines a weakly informative prior for enadenotucirev with toxicities from a range of doses observed in set of enadenotucirev studies,

and then adding an extra layer of variability to account for heterogeneity among subjects receiving a single dose vs subjects receiving >1 doses in the enadenotucirev studies. Note that this weakly informative prior is for enadenotucirev and is different from the weakly informative prior for BMS-986277 described in [Section 1.2](#).

- Weakly informative prior for enadenotucirev:
  - The median toxicity rate at the enadenotucirev reference dose ( $1 \times 10^{13}$ ) was assumed to be 30%, ie,  $\text{mean}(\log(\alpha_1)) = \text{logit}(0.30) = -0.847$ .
  - A doubling in dose was assumed to double the odds of DLT, ie,  $\text{mean}(\log(\beta_1)) = 0$ .
  - The standard deviation of  $\log(\alpha_1)$  was set to 2, and the standard deviation of  $\log(\beta_1)$  was set to 1, which allows for considerable prior uncertainty for the dose-toxicity profile.
  - The correlation between  $\log(\alpha_1)$  and  $\log(\beta_1)$  was assumed to follow a uniform(-1, 1) distribution with mean 0 (assuming independence of  $\log(\alpha_1)$  and  $\log(\beta_1)$ ).
- Dose-toxicity data:
  - Two studies of enadenotucirev monotherapy have been completed in patients with a range of epithelial solid cancers. The first evaluated escalating doses of intravenous enadenotucirev and repeat cycle schedules (ColoAd1-1001); the second was a mechanism of action study with administration of a single cycle of intratumoral or intravenous enadenotucirev (ColoAd1-1002).
  - In these studies, a total of 73 subjects received intravenous enadenotucirev for a range of doses, cycles, and schedules
  - In ColoAd1-1001:
    - ◆ During the initial dose escalation evaluation, enadenotucirev was given on Days 1, 3, and 5 at doses ranging from  $1 \times 10^{10}$  to  $1 \times 10^{13}$  viral particles (vp) per administration.
    - ◆ Subsequently, repeat cycles with a three-weekly schedule (21-day cycle) were evaluated with doses of  $1 \times 10^{12}$  to  $6 \times 10^{12}$  vp per administration given on Days 1, 3, and 5 of each cycle.
    - ◆ Additionally, a weekly dosing schedule was investigated at doses of  $3 \times 10^{12}$  and  $6 \times 10^{12}$  where treatment was administered on Days 1, 3, 5, 8, and 15 in the first cycle and on Days 1, 8, and 15 in subsequent cycles.
  - In ColoAd1-1002: a single cycle of enadenotucirev at a dose of  $1 \times 10^{12}$  vp was given on Days 1, 3, and 5.
  - Across ColoAd1-1001 and ColoAd1-1002, 40 subjects received 1 cycle of enadenotucirev and 33 subjects received >1 cycle
  - Two subjects experienced similar DLTs after the first dose of enadenotucirev at  $1 \times 10^{13}$  vp. One subject experienced hypoxia and dyspnoea and the second subject experienced acute

lung injury. These events were all considered Grade 3 per the NCI CTCAE, definitely related to treatment, and resulted in discontinuation of treatment.

- The data are summarized in Table 1.

**Table 1: Data from ColoAd1-1001 and ColoAd1-1002**

Dose of BMS-986277 (vp)	Dose of Enadenotucirev (vp)	DLT (percentage [number of participants/total participants])		
		Single Dose	Multiple Dose	Total
3x10 	1x10 	0% (0/3)		0% (0/3)
	1x10 	0% (0/3)		0% (0/3)
3x10 	1x10 	0% (0/15)	0% (0/3)	0% (0/18)
1x10 	3x10 	0% (0/6)	0% (0/14)	0% (0/20)
3x10 	6x10 	0% (0/10)	0% (0/15)	0% (0/25)
	1x10 13*	67% (2/3)	0% (0/1)	50% (2/4)

\*Enadenotucirev reference dose

In addition, heterogeneity between the historical study and the current study was incorporated using a MAP, by defining between-trial standard deviations  $\tau_1$  and  $\tau_2$  for  $\log(\alpha_1)$  and  $\log(\beta_1)$ , respectively. The between-trial variability is assumed to be moderate, therefore,  $\tau_1$  and  $\tau_2$  were set to follow a log-normal distribution with mean  $\log(0.25)$  and  $\log(0.125)$  respectively with a common standard deviation  $\log(2)/1.96$ .

### 1.2.2 Weakly Informative Prior for BMS-986277 Component

- The median toxicity rate at the BMS-986277 reference dose (3x10^12) was assumed to be 30%, ie, mean ( $\log(\alpha_1)$ ) =  $\text{logit}(0.30) = -0.847$ .
- A doubling in dose was assumed to double the odds of DLT, ie, mean( $\log(\beta_1)$ ) = 0.
- The standard deviation of  $\log(\alpha_1)$  was set to 1.53 using the following steps:
  - If the toxicity probability range was set to be [1%, 99%], then the toxicity interval would be  $\text{logit}(0.99) - \text{logit}(0.01) = 9.19$ .
  - To cover 99.7% of the variance, the toxicity interval will cover  $6 \cdot \text{sd}(\log(\alpha_1))$ , which results in  $\text{sd}(\log(\alpha_1)) = 9.19/6 = 1.53$ .
- The standard deviation of  $\log(\beta_1)$  was set to 2, which allows for considerably large prior uncertainty for the dose toxicity relationship.

- The correlation between  $\log(\alpha_1)$  and  $\log(\beta_1)$  was assumed to follow a uniform(-1, 1) distribution with mean 0 (assuming independence of  $\log(\alpha_1)$  and  $\log(\beta_1)$ ).
- $\log(\alpha_1)$  and  $\log(\beta_1)$  follow a bivariate normal distribution.

### 1.2.3 Mixture Prior

To obtain the mixture prior, 50% weight is assigned to the MAP component (described in Section 1.2.1), and 50% weight is assigned to the weakly informative component (described in Section 1.2.2) to balance the previous experience with enadenotucirev and potential unknown toxicity profile of BMS-986277.

The mixture prior will be fitted into EAST® v6.3.1 Dose Escalation Module by Cytel for the Monotherapy Escalation (Part 1A) as stated in model setup section.

The mixture prior with both MAP and weakly informative components for the BLRM parameters of BMS-986277 is generated using R v3.4.1 and R2OpenBUGS package v3.2 and summarized in Table 2.

**Table 2** Prior Distribution for Model Parameters ( $\log(\alpha_1)$ ,  $\log(\beta_1)$ ) for BMS-986277

Parameter	Means	Standard Deviations	Correlation
MAP component	(-1.065, 1.786)	(1.005, 0.697)	0.470
Weakly informative prior for BMS-986277 component	(-0.847, 0)	(1.53, 2)	0
Mixture Priors for BMS-986277	(-0.959, 0.884)	(1.005, 1.240)	0.055

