## 2 DOSE ESCALATION PROCESS AND SIMULATIONS IN MONOTHERAPY

### 2.1 Dose Escalation Process

Dose escalation recommendations for BMS-986277 monotherapy will be based on the inference from the Bayesian posterior and the probability that the true DLT rate for each dose lies in 1 of the following categories:

- [0%, 16%) under-dosing
- [16%, 33%) targeted toxicity
- [33%, 100%] excessive toxicity

Note: “[” or “[” is inclusive of the respective endpoint, and “(” or “)” exclusive of the respective endpoint.

These boundaries are similar to the toxicity boundaries used by a rule-based design (ie, 3 + 3 design) in that a minimum is set at 16% (~ 1 in 6) DLT rate and a maximum at 33% (~ 2 in 6) DLT

rate. Following the principle of EWOC, dose recommendations for the next cohort will be based on the Bayesian model after DLT information becomes available during the DLT period, accounting for all of the available data from the administered doses, and the candidate doses for the next cohort are the ones fulfilling the overdose criterion that there is no greater than 35% chance of excessive toxicity. Only the candidate doses will be considered for the next cohort. While the Bayesian model will use DLT information from the DLT period only, clinical assessment will take into consideration the totality of available data including PK/pharmacodynamics from all treated participants.

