## **2.2 Simulation Parameters**

Simulation study was done for monotherapy dose escalation using various hypothetical scenarios. One thousand trial simulations were used for each scenario. All simulations were run using EAST 6.3.1® software BLRM module for BMS-986277 monotherapy. The number of participants to be

treated in each cohort in a specific dose level, the stopping rules used to identify the BLRM-RD, and other simulation parameters are defined as:

- Fixed cohort size: 3
- Probability of overdosing:  $\leq 35\%$
- Target probability of toxicity: 0.33, the upper boundary of the targeted toxicity interval
- Probability of achieving the target toxicity:  $> 50\%$
- Maximum number of participants treated: 24
- Prior specification on model parameters:
  - Mean:  $\log(\alpha_1) = -0.959$ ,  $\log(\beta_1) = 0.884$
  - Variance:  $\log(\alpha_1) = 1.010$ ,  $\log(\beta_1) = 1.537$
  - Correlation: 0.055
- Posterior sampling method: Metropolis Hastings
- Minimum number of participants treated at a given dose level in order to identify the BLRM-RD: 6
- Maximum number of participants at a dose: 12

The provisional dose levels for BMS-986277 monotherapy are  $3 \times 10^{10}$ ,  $3 \times 10^{11}$ ,  $1 \times 10^{12}$ , and  $3 \times 10^{12}$  vp, with  $3 \times 10^{12}$  as the reference dose (dose expected to have 30% DLT).

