### Interpretation and Use of [Figure 2](#):

[figure not shown]
Figure 2 is a snapshot of stacking histogram with DLT information available at dose level  $3 \times 10^{10}$  vp and  $3 \times 10^{11}$  vp. This figure will be updated each time new DLT information becomes available.

When recommending the next dose level, the model will first exclude doses that are intolerable (with overdosing probabilities > 35%, the rate that has been specified for BMS-986277). Among those qualified candidate doses that are considered “tolerable”, the model will select the dose that maximizes the probability of being within the target toxicity range (DLT rate between 16% and 33%). However, there will be no dose skipping during the dose escalation monotherapy phase of the study.

As illustrated in Figure 2, the distribution of predicted DLT rates will be characterized into possibilities falling into 3 different categories. First, dose levels  $3 \times 10^{12}$  vp for BMS-986277 are excluded according to the higher-than-cutoff overdosing probabilities (0.579 for  $3 \times 10^{12}$  vp). Among the remainder of tolerable dose levels, the BLRM recommends the dose that maximizes the probability of being within the target dosing interval. Therefore, the model’s recommendation would be to stay at  $1 \times 10^{12}$  vp, which is associated with the highest target dosing probability of 0.418 compared with that of  $3 \times 10^{10}$  vp (0.068) and  $3 \times 10^{11}$  vp (0.254).

Similarly (although not shown on Figure 2), according to the rules specified above, the model could possibly recommend to de-escalate to a lower dose level than the current treated dose level, escalate to the next dose level, or even recommend to stop and identify a new dose level lower than  $3 \times 10^{10}$  vp, the lowest pre-specified dose level. Please refer to the description of [Figure 1](#) for details on how to specify the new dose levels.

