**3.1 Example of using the BLRM for BMS-986277 Monotherapy Dose Escalation**

[figure not shown]
According to safety consideration and clinical judgement, the dose level  $3 \times 10^{10}$  vp is recommended as the starting dose for BMS-986277 monotherapy. With the current BMS-986277 prior specified in the Section 1.2 and all available DLT information up to  $3 \times 10^{12}$  vp, a

corresponding decision tree illustrating various models' recommendations under all possible scenarios for the first two cohorts is provided in Figure 4.

Tracing a branch of the decision tree in Figure 4 illustrates the decision making process. Taking the left-most branch of the tree as an example, starting at  $3 \times 10^{10}$  vp, if there were 0 DLTs observed in the real clinical trial, the model would recommend to escalate to  $3 \times 10^{11}$  vp (the BLRM actually recommends escalating to the highest dose  $3 \times 10^{12}$  vp, but since this is a 100-fold increase of dose and dose skipping is not allowed, the dose level  $3 \times 10^{11}$  vp is selected), one level above the current treated dose level according to the escalation rules per protocol. Next, if there is 0 DLTs observed at  $3 \times 10^{11}$  vp, the model would recommend to escalate further to  $1 \times 10^{12}$  vp. At  $1 \times 10^{12}$  vp, there would be 3 potential decisions (0/3 escalate, 1/3 and 2/3 would stay, and 3/3 would de-escalate); this is not shown due to crowding the diagram.

During the actual clinical study, the tree would be narrowed or deepened based on actual DLTs observed. The clinical team will be able to leverage this decision tree to preview decisions at each interim monitoring step and to plan proactively.

**Figure 4: The BLRM Model Hypothetical Decision Tree for BMS-986277 Monotherapy during Dose Escalation (for the first 2 cohorts)**

Abbreviations: DE = de-escalation; E = escalation; S = stay.

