#### 4.2.3 *Prior for Interaction Parameters for Joint Toxicity of BMS-986277 and Nivolumab Combination*

A gamma prior distribution for the interaction parameter  $\gamma$  is derived to reflect the current uncertainty about the toxicity profile of the combination of BMS-986277 and nivolumab. Although no pharmacokinetic (PK) drug-drug interaction is expected, the possibility of a significant positive interaction between BMS-986277 and nivolumab cannot be totally excluded. The interaction parameter  $\gamma$  was chosen accordingly but with a degree of uncertainty to allow for the possibility that the interaction may be positive or negative. Therefore, the following assumptions are made for the interaction parameter:

- $\gamma$  follows a gamma distribution with a mean centered at 1.2, which means the combination of 2 agents is likely to have only a small synergistic effect.
- The standard deviation of  $\gamma$  is 0.5 such that there is a 61% prior probability that  $\gamma$  is larger than 1.

This model assigns the highest probability to there being small synergistic interaction and also allows for the potential of larger synergism of the toxic profiles. It also does not completely ignore the possibility of antagonism because there is a 39% prior probability that  $\gamma$  is less than 1.

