**Table 6: Data from ColoAd1-1003**

Dose of Enadenotucirev (vp)	DLT (percentage [number of participants/total participants])		
	1 Cycle	2 Cycles	Total
$1 \times 10^{12}$	33% (2/3 pembro + 0/3 nivo)	11% (1/9)	20% (3/15)
$3 \times 10^{12}$	0% (0/3)	Ongoing	0% (0/3)

After incorporating the combination data, the BLRM-Copula provides the following parameter estimates shown in Table 7, which will be used as the prior for BMS-986277 in combination with nivolumab.

**Table 7: Prior Distribution for Model Parameters for BMS-986277 in Combination with Nivolumab (ie, Posterior from EnAd in Combination with PD-1 Inhibitor)**

Parameter	Means	Standard Deviations	Correlation
$\log(\alpha_1), \log(\beta_1)$ - BMS-986277	(-1.653, 0.8457)	(0.8304, 1.484)	0.145
$\log(\alpha_2), \log(\beta_2)$ - Nivolumab	(-1.852, -2.135)	(0.1621, 0.3025)	-0.04503
$\gamma$	1.021	0.399	

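### Protocol Appendix 9, Table 2: the printed mixture prior (SDs 1.005, 1.240) is not the 50/50 mixture of its stated components (SDs 1.299, 1.744), and the tighter prior feeds the Part 1 simulations and the worked example

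*Protocol*

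**What the plan says.** All section and table numbers here are in Protocol Appendix 9 unless stated.

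Section 1.2.3 defines the Part 1 prior: "50% weight is assigned to the MAP component (described in Section 1.2.1), and 50% weight is assigned to the weakly informative component". Table 2 lists, for (log α1, log β1):

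| Row | Means | SDs | Correlation |
|---|---|---|---|
| MAP component | -1.065, 1.786 | 1.005, 0.697 | 0.470 |
| Weakly informative component | -0.847, 0 | 1.53, 2 | 0 |
| Mixture | -0.959, 0.884 | 1.005, 1.240 | 0.055 |

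Section 1.2.2 derives the 1.53 step by step (9.19/6) and says the SD of log(β1) "was set to 2, which allows for considerably large prior uncertainty for the dose toxicity relationship". Section 2.2 enters the mixture row in the simulations as variances 1.010 and 1.537.

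Section 2.1 admits as candidates only doses for which "there is no greater than 35% chance of excessive toxicity", meaning a true DLT rate of 33% or more. In the Figure 2 example (0/3 at 3×10^10, 1/3 at 3×10^11) the model recommends 1×10^12 vp, "which is associated with the highest target dosing probability of 0.418". Section 3.1 gives the decisions at 1×10^12 vp after two clean cohorts: "0/3 escalate, 1/3 and 2/3 would stay, and 3/3 would de-escalate".

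**The concern.** Section 1.2 adds the weakly informative component because BMS-986277 may be more toxic than enadenotucirev. If the mixture used is narrower than the one described, part of that allowance is lost. The model is then more confident in advance that low doses are safe, and the overdose criterion takes more DLTs to respond. This prior enters every Part 1 model recommendation in a first-in-human study, and Table 3, Figures 1 to 4 and the decision tree all depend on it.

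**Working it through.** **1. Mixture moments.** With weights of one half, variance = 0.5(s1² + s2²) + 0.25(m1 − m2)².

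- Means: (−1.065 − 0.847)/2 = −0.956; (1.786 + 0)/2 = 0.893. Printed: −0.959, 0.884. These agree.
- log(α1): 0.5(1.010 + 2.341) + 0.25(0.218²) = 1.687, SD 1.299. Printed: 1.005.
- log(β1): 0.5(0.486 + 4) + 0.25(1.786²) = 3.040, SD 1.744. Printed: 1.240.
- Covariance: 0.5(0.470 × 1.005 × 0.697) + 0.25(−0.218)(1.786) = 0.067. Correlation: 0.067/(1.299 × 1.744) = 0.030. Printed: 0.055.

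**2. This is not rounding.** The weak component alone contributes 0.5 × 1.53² = 1.170 and 0.5 × 2² = 2 to the variances. The mixture SDs therefore cannot be below 1.08 and 1.41, whatever the MAP component is. Both printed values are lower.

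**3. What reproduces the printed row.** Other weights (0.4 to 0.9), averaging draws or SDs, and reading 1.53 and 2 as variances or precisions all fail. A weak component with SDs (1, 1) gives SDs 1.008 and 1.241 and correlation 0.054, almost exactly the printed row. That is an inference about the cause, and it conflicts with Section 1.2.2.

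**4. The printed row was used.** 1.005² = 1.010 and 1.240² = 1.538, which are the Section 2.2 inputs up to rounding. For Figure 2, I integrated the posterior on a grid with logit(p) = log(α1) + β1·log(dose/3×10^12).

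| Quantity | Document | Printed prior | Actual mixture |
|---|---|---|---|
| Target probability, 3×10^10 | 0.068 | 0.068 | 0.177 |
| Target probability, 3×10^11 | 0.254 | 0.257 | 0.334 |
| Target probability, 1×10^12 | 0.418 | 0.415 | 0.355 |

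The overdose probability at 3×10^12 is 0.563 with the printed prior, against 0.579 stated. The example was therefore produced with the tighter prior, or one very close to it.

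**5. Effect on the overdose criterion.** P(DLT rate ≥ 33%), to compare with 0.35:

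| Data | Dose assessed | Printed prior | Normal, correct moments | Actual mixture |
|---|---|---|---|---|
| 1/3 at 3×10^10 | 3×10^11 | 0.24 | 0.38 | 0.47 |
| 2/3 at 3×10^10 | 3×10^10 | 0.34 | 0.58 | 0.71 |
| 0/3, then 2/3 at 3×10^11 | 3×10^11 | 0.24 | 0.37 | 0.46 |
| 0/3, 0/3, then 2/3 at 1×10^12 | 1×10^12 | 0.24 | 0.34 | 0.40 |

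The first three cross the cap under either correction. In the second, no planned dose remains under it, which is the all-doses-intolerable rule of Section 2.1. In the fourth, the Section 3.1 decision to stay passes under the correct-moment normal and fails only under the actual mixture.

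In the Figure 2 example the overdose probability at 1×10^12 becomes 0.31 (normal) or 0.34 (mixture). Both are under the cap, and that dose still has the highest target probability, so the recommendation is unchanged.

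**6. Table 7, separately.** The nivolumab SDs are printed as "0.1621, 0.3025". Table 5 gives SDs 0.404 and 0.546, whose squares are 0.163 and 0.298. Eighteen binary outcomes add at most 18 × 0.25 = 4.5 units of information, so the SD of log(α2) should not fall much below 1/√(1/0.404² + 4.5) = 0.307. For log(β1), 1.484 exceeds its printed prior SD of 1.240; read as a variance it gives SD 1.218. The γ entry differs. Its prior SD "is 0.5 such that there is a 61% prior probability that" γ exceeds 1, and 0.399 read as a variance would give SD 0.632, above that 0.5. It therefore reads as an SD. The entry 0.8304 fits either scale.

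**The case against.** Four points on the other side carry weight.

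- The direction of the error is open. If SDs of (1, 1) were intended, only Section 1.2.2 and the component row of Table 2 are wrong, and the simulations stand. The derivation of 1.53 argues against this but does not settle it.
- Section 2.2 supplies the software with one set of means, variances and a correlation. The like-for-like correction is then the normal with correct moments, which is milder than the full mixture.
- In an approximate rerun of the five Table 3 scenarios without dose skipping, the overall observed DLT rate moved by no more than about one percentage point under either correction.
- Clinical assessment of all data, no dose skipping and staggered dosing also limit exposure. They do not replace the cap, because Section 2.1 draws the next dose only from those that pass it.

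Two stronger readings are tempting and are not supported. One is that every early-DLT case changes, including the Section 3.1 decision to stay after 2/3 at 1×10^12. That holds only for the full mixture. The other is that Table 7 also weakens overdose control in Part 2. The documents do not show whether its values were entered as SDs or only mislabelled, and the copula formula is redacted. They also do not state the PD-1 inhibitor dose in the 18 combination participants, three of whom received pembrolizumab. Sections 4.2, 4.2.1 and 5.1 make that prior provisional.

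**Conclusion.** Table 2 is wrong as written. The mixture SDs should be 1.299 and 1.744 (variances 1.687 and 3.040) with correlation 0.030, if the component rows and weights are right. The printed row feeds the simulations and the worked example, so this is more than a misprint in one table.

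The effect is concentrated in DLTs at 3×10^10 and 3×10^11 vp. There the overdose probability rises from 0.24–0.34 to 0.37–0.58 under the milder correction and to 0.46–0.71 under the actual mixture. At 1×10^12 it depends on which correction is used. These figures assume the logistic form with reference dose 3×10^12 vp, which the match to Figure 2 supports, and the 35% cap in the protocol. SAP Section 6.1 gives that cap as 25% in one sentence and 35% in another; those must be reconciled too.

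The Table 7 point is a plausible inference about three entries and does not bear on the conclusion above.

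**What to change.** Reconcile Sections 1.2.2, 1.2.3 (Table 2) and 2.2.

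- If 1.53 and 2 stand: carry the two-component mixture, or use SDs (1.299, 1.744) and correlation 0.030. State which. Update the Section 2.2 inputs and rerun Table 3, Figures 1 to 4 and the decision tree.
- If (1, 1) was intended: correct Section 1.2.2 and the component row of Table 2, and give the rationale. The simulations then stand.

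For Table 7, the sponsor should confirm the scale of each entry and what was entered in the Part 2 model, and relabel as needed. Table 8 needs rerunning only if variances were entered as SDs.

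The cost is a few hours of programming and a correction to the appendix, with no additional participants. Some stated operating characteristics will change if the wider prior is adopted.
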